In group-level randomized trials design such as PIC and CPIC, the power analysis is complex because there are many factors that influence power^{176, 177}. For a simple group-level randomized trial, the power of a test such as a t-test in comparing two group means is a function of the cluster size (m), the number of clusters (J), and the intra-class correlation (ICC), the ratio of the between-cluster variability between clusters to the total variability. In our application where cluster is organization unit, we use Kish's method^{176, 177} to adjust the standard errors by the variance inflation factor (VIF) defined as $VIF=1+(m-1)\times ICC$, where ICC is the intra-class correlation at the organization unit level. For analysis of repeated measures, we use an extended formula accounting for inter-temporal correlations within individuals and within units¹⁷⁷. Based on PIC data, outcome analyses on depression care and clinic outcomes have shown that the ICC at the clinic level is either absent or around 0.01, and inter-temporal correlation coefficients within individuals and within units over a 12-month time period are greater than 0.60. PIC provider data shows that ICCs are nearly absent for provider experience and around 0.00-0.05 for knowledge. Taking a conservative approach, we assume that ICC at the unit level ranges from 0.00 to 0.02 for client data and from 0.00 to 0.05 for provider data, and that the inter-temporal correlation is 0.50. In the calculation of power for testing intervention effects from a t-test, we use degrees of freedom equal to (number of clusters – 2) when $ICC>0$, which is conservative for assessing significance, although we also explore setting degrees of freedom equal to $N-2$ (N =total sample size) for the scenario where $ICC=0$ (the optimistic scenario). We also note that regression analyses adjusting for baseline covariates and stratification variables can improve statistical power if covariates explain a substantial portion of the uncertainty.¹⁷⁷ All power analyses are conducted with power of 80% or above as adequate, assuming two-sided tests with significance level 0.05. For client data, we provide detailed power analysis for two primary study variables (appropriate depression care and probable depression).

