Unit-Level Multiple Imputation We used a hot deck multiple imputation procedure based on an approximate Bayesian bootstrap method for unit-level missing data.^{12, 13} This model assumes that both missingness and dropout arise from mechanisms that are missing at random (MAR) in the sense defined by Rubin. Our imputation techniques attempted to include information related to the missing values whenever possible. We first modeled the propensity of response at a given time point (coded 1 if response and 0 if nonresponse). In Step 2, we stratified cases based on the quintiles of the propensity scores and used the approximate Bayesian bootstrap to select donors. In practice these procedures were applied in sequence for the baseline, 6-month, 12-month, and 3-year data, with imputations stratified by two intervention arms. We started with imputing baseline. For each of the 5 item-level imputed screener datasets, we imputed a unit-level imputation baseline dataset. Limited to the analytic sample of 1,018, we then used baseline variables as predictors for modeling 6 and 12-month follow-up data and produced unit-level imputation datasets. In modeling the logistic regression of predicting response propensities, we started with a large set of independent variables. The final baseline model included the predictors: age, gender, ethnicity, income, living situation, US born, community, and type of

screening program. The 6-month models included participants characteristics assessed at screener (age, gender, ethnicity, health insurance, and type of screening program.), and baseline clinic and service variables (multiple chronic conditions, alcohol abuse or use of illicit drugs, any depression care). The 12-month models included additional variables: community, PHQ-8 assessed at screener, mental wellness, homeless status at baseline. The 3 years models included age, gender, ethnicity, employment status, ≥ 3 chronic conditions, homeless, 12-month alcohol abuse or use of illicit drugs, no place to stay for at least two nights in the past 6 months, type of screening program, and community with additional stratum variable sector (social-community screening sector vs healthcare Screening Sector) in Step 2. Values for participants who were deceased were not imputed.

A4. Analyses

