For all study components (including supplement components discussed below), we convened working groups co-chaired by academic and community members to review analysis plans, data output and discuss findings.

Analyses for 6-month outcome: We conducted intent-to-treat, comparative-effectiveness analyses with intervention status as the independent variable, using logistic regression for dichotomous measures and Poisson regression models for count variables. Covariates were selected to account for known associations of sociodemographic and clinical status indicators with primary outcome measures. We adjusted for baseline status of dependent variables and covariates (age, sex, ≥ 3 chronic general medical conditions from a list of 18, education, race/ethnicity, family income < federal poverty level, 12-month alcohol abuse or use of illicit drugs at baseline, 12-month depressive disorder at baseline, and community). All analyses were conducted using SUDAAN Version 10.0 (<http://www.rti.org/sudaan/>) and accounted for clustering (clients within programs), weighting, and multiple imputations. Significance of comparisons by intervention status was based on regression coefficients. Results of logistic regression models are presented as odds ratios (OR) and Poisson models as rate ratios (RR) with 95 % confidence intervals. We illustrate results for intervention groups adjusted for covariates using standardized predictions generated from fitted regression models.¹⁴ We present Cohen's effect size index h , defined for dichotomous variables,¹⁵ where $h=0.20$ is small, $h=0.50$ is medium and $h=0.80$ is large. We supplement adjusted models with unadjusted raw data to assess

robustness. We applied a Bonferroni adjustment considering two primary outcomes (Poor mental health qualify of life $MCS-12 \leq 40$, and at least mild depression $PHQ-9 \geq 10$) and compared the proportion of results across outcomes favoring one intervention to an assumed null-hypothesis of 0.5.

Analyses for 12-month outcome: We conducted intent-to-treat analyses of repeated measures including all participants with available data at baseline, 6-, or 12-months by using SAS software version 9.2 (SAS Institute). We used a model-based approach with unweighted data. Initial explorations of 3-level, random-effects logistic models using SAS PROC GLIMMIX for binary outcomes yielded unstable estimates for program-specific random effects.^{16, 17}

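### Unit-level hot-deck donors ignore the client's program, so the program-clustered standard errors at 6 months and 3 years are slightly too small

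*Combined protocol and SAP*

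**What the plan says.** Appendix A3 (Unit-Level Multiple Imputation) models the probability of response at each wave, and then "we stratified cases based on the quintiles of the propensity scores and used the approximate Bayesian bootstrap to select donors". The procedure runs "with imputations stratified by two intervention arms". The 6-month response model uses screener characteristics ("age, gender, ethnicity, health insurance, and type of screening program") and some baseline clinical and service variables. Community is added at 12 months and kept at 3 years, and a two-level sector stratum is added for donor selection at 3 years. The individual program is not listed as a predictor, a donor stratum or a bootstrap unit. Five completed datasets result ("For each of the 5 item-level imputed screener datasets").

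Appendix A4 states that the 6-month analyses "accounted for clustering (clients within programs), weighting, and multiple imputations". The 3-year endpoint analysis refers back to the same strategy.

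Section 5 (Power for 6-Month Client Outcomes Analyses) treats program clustering as something to allow for. It says of the planning value: "we assume that ICC at the unit level ranges from 0.00 to 0.02 for client data". For the prior study it reports that "the ICC at the clinic level is either absent or around 0.01".

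**The concern.** Programs were randomized, so the variance of the CEP-RS difference must include between-program variation. An imputed client receives an outcome from a donor who may belong to any program in the same arm and propensity class. That outcome is nearly unrelated to those of the client's own program, so within-program correlation in the completed data is diluted.

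A clustered variance estimator measures only the correlation it finds, so it cannot restore what the imputation removed. Rubin's between-imputation term does not restore it either, because the bootstrap resamples donors and not programs. The error runs one way: intervals too narrow and tests too liberal in the weighted endpoint analyses of both primary outcomes. None of the listed sensitivity analyses isolates it.

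**Working it through.** **Inputs.**
- 6 months: 1,018 analysed (A2) and 759 completers (A1), so 259/1,018 = 25% are imputed. The arm counts in A1 sum to 380 + 359 = 739, which would give 27%.
- 3 years: 980 analysed (A2) and 600 completers, so 380/980 = 39% are imputed.
- 89 programs (Section 6, Methods), so m = 1,018/89 = 11.4 and 980/89 = 11.0 clients per program.
- ICC 0.00 to 0.02 (Section 5).

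**The plan's own figure.** The minimum detectable effect is (critical value + power quantile) × √(4/N × VIF), with VIF = 1 + (N/J − 1) × ICC and J programs. For N = 780 this gives 0.2006 at ICC 0, and 0.216 (J = 100) to 0.220 (J = 80) at ICC 0.02. Table 4 states 0.20-0.22, so the plan's clustering model is reproduced.

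**Closed form, equal program sizes.** Let p be the response rate.
- True variance of an arm mean is proportional to (1/p) × [1 + (mp − 1) × ICC], because the information comes from mp respondents per program.
- In the completed data, two clients of one program share its effect only if both responded (probability p²). The clustered within-imputation part is 1 + (m − 1) × ICC × p².
- The between-imputation part adds about (1 − p)/p.
- The sum equals (1/p) × [1 + (m − 1) × ICC × p³].

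Reported/true variance is therefore [1 + (m − 1) × ICC × p³] / [1 + (mp − 1) × ICC].

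| Wave | p | ICC | Variance ratio | SE shortfall |
|---|---|---|---|---|
| either | – | 0 | 1 | 0% |
| 6 months | 0.746 | 0.01 | 1.0433/1.0753 = 0.970 | 1.5% |
| 6 months | 0.746 | 0.02 | 1.0865/1.1506 = 0.944 | 2.8% |
| 3 years | 0.612 | 0.01 | 1.0230/1.0574 = 0.967 | 1.6% |
| 3 years | 0.612 | 0.02 | 1.0460/1.1148 = 0.938 | 3.1% |

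Using 739 completers moves the 6-month shortfall at ICC 0.02 only to 2.9%.

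**Simulation.** Settings: 89 programs, no true effect, donors by approximate Bayesian bootstrap within arm and five classes, five imputations, clustered variance, Rubin's rules. A complete-case clustered analysis of the same data is the control, and net shortfall = 1 − (imputed ratio / control ratio). Even sizes used 16,000 runs per setting. The assumed coefficient of variation (CV) of 0.7 used 5,000 runs, which puts about 1% Monte Carlo error on a ratio.

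| Wave | Sizes | ICC | Reported/true SE | Control | Net shortfall | Type I error |
|---|---|---|---|---|---|---|
| 6 months | even | 0.01 | 0.982 | 0.998 | 1.6% | 5.5% |
| 3 years | even | 0.01 | 0.975 | 1.001 | 2.6% | 5.6% |
| 6 months | even | 0.02 | 0.969 | 1.000 | 3.1% | 6.0% |
| 3 years | even | 0.02 | 0.974 | 1.010 | 3.6% | 5.7% |
| 6 months, binary | CV 0.7 | 0.01 | 0.976 | 1.000 | 2.4% | 5.0% |
| 3 years, binary | CV 0.7 | 0.01 | 0.969 | 0.997 | 2.8% | 6.3% |
| 6 months, binary | CV 0.7 | 0.02 | 0.951 | 1.000 | 4.9% | 6.6% |
| 3 years, binary | CV 0.7 | 0.02 | 0.950 | 0.997 | 4.7% | 6.1% |
| 3 years, normal | CV 0.7 | 0.02 | 0.943 | 0.986 | 4.4% | 6.3% |

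At ICC 0 the 3-year runs showed no shortfall beyond the control, within Monte Carlo error.

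**Consistency.** A standard error too small by a fraction s gives a two-sided error of 2 × [1 − Φ(1.96 × (1 − s))]. That is 5.7% at s = 3%, 6.3% at 5% and 6.5% at 6%.

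**The case against.** The strongest reply is that the effect is too small to matter, and much of that reply stands. The prior study's ICC was zero or about 0.01, where the shortfall is 3% or less. The primary outcomes are analysed with adjustment for their baseline value and community. If program differences are stable over time, that adjustment removes part of the between-program variation and shrinks the shortfall. Program type and community in the response models may also retain a little of it. Unadjusted raw data are presented as a check, and a 3-year longitudinal sensitivity analysis models program-level correlation. The 6-month primary outcomes carry a Bonferroni adjustment and the 3-year outcomes a false-discovery-rate adjustment, so 5% is not the only operating level.

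These points limit the size but do not remove the defect. The raw-data comparison also drops the covariates, so it cannot show what the imputation did to the variance. Multiplicity adjustments presuppose valid p-values.

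A reader might go further and infer that standard errors are 4-7% too small throughout the planned ICC range, with false positives up to 8%. The documents do not support that:
- At ICC 0 there is no clustering to lose.
- A shortfall above 4% needs an ICC near 0.02 and markedly uneven programs, and the documents give no distribution of program sizes.
- An 8% error rate needs a standard error about 10.7% too small.
- At an assumed CV of 1.0, type I error reached 6.4-7.3%. However, the complete-case control also fell short by 1-3 points, which comes from the clustered variance estimator and not from the imputation.

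**Conclusion.** Wrong as written, but minor in size. Donor selection ignores the randomized unit, and the clustered standard errors are biased downward whenever the ICC exceeds zero.

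- ICC 0: no understatement.
- ICC 0.01: about 1.5-3%.
- ICC 0.02, even program sizes: about 3-4%.
- ICC 0.02, uneven sizes (CV 0.7): up to about 5-6%, of which 4-5% is net of the control.
- Nominal 5% tests: about 5-6.5%.

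The assumptions are missingness unrelated to outcome, random classes in place of propensity quintiles, no weights and no baseline adjustment. The documents report neither program sizes nor an ICC observed in this trial, so the position within these ranges is unknown. The finding does not show that any reported CEP-RS difference is false, nor that clustering was ignored. It was allowed for, but on data in which the imputation had weakened it.

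**What to change.** For the two primary outcomes at 6 months and 3 years, do one of the following:

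1. Impute the continuous MCS-12 and PHQ scores within arm from a linear model with a program random intercept, then dichotomize. In simulation with a normal outcome this gave a reported/true SE ratio of 0.98-1.01 and type I error of 5-6% at ICC 0.01-0.02. Working on the continuous scale avoids the unstable program effects that A4 reports for random-effects logistic models.
2. Keep the hot deck and take the variance from a bootstrap that resamples whole programs within arm and repeats imputation and estimation each time. This gave an SE ratio of 1.00-1.02. It also keeps whole donor records, and so the associations among outcomes.

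Two apparent shortcuts should be avoided. A delete-one-program jackknife with fresh random imputation in each replicate multiplies the imputation noise, and its standard errors were 2.1-2.6 times too large. Restricting donors to the client's own program made them 11-17% too large.

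Report the observed program ICC and the distribution of program sizes as well, so that readers can place the trial within the ranges above. No new data are needed. The cost is extra analysis and computing, and slightly wider intervals.

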With further 20% expansion, final	780	0.20-0.22	9.98-10.92%

†Detectable effect size (mean difference between two groups divided by the standard deviation)¹⁷⁸. §Detectable percentage point difference for two groups.

6. CPIC 3-Year extension (PCORI award # 1845)

Background: Depression is a leading cause of morbidity with disparities in care. Depression collaborative care, a team-based approach supporting care management, patient activation and evidence-based treatments, is effective relative to usual care but often unavailable in under-resourced communities. Community Partners in Care (CPIC) randomized 95 programs in healthcare and community-based (e.g., social services, faith-based) service sectors in two communities to Resources for Services (RS) for individual program technical assistance versus

Community Engagement and Planning (CEP) for multi-sector coalition support for depression collaborative care. For depressed clients, CEP relative to RS reduced having poor mental health-related quality of life (MHRQL) and behavioral health hospitalization over 6-12 months. Longer-term outcomes are unknown.

Aims: This extension study of CPIC aims to:

1. Compare CEP and RS effects at 3-year follow-up, 2-years after intervention support, on primary (depression and MHRQL), community-prioritized outcomes of physical health-related quality of life (PHRQL) and behavioral health hospitalization, and outpatient services use (secondary);
2. Compare effects of CEP and RS at 6, 12, and 36 months for CPIC participants enrolled in healthcare or community-based service sectors;
3. Describe outcome priorities for African American and Latino depressed clients, and as perceived by providers.
4. Describe views of stakeholders planning the Los Angeles County Health Neighborhood Initiative (HNI) informed by CPIC; and national stakeholders briefed on CPIC and HNI.

We hypothesized that CEP relative to RS would improve long-term mental and physical health and reduce hospitalization nights, overall and within sector. We expected stakeholders to prioritize social factors and mental health.

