Methods: Extension Study (Aims 1-3): Between 1/2014-10/2014, we approached 1004 CPIC clients initially screened as depressed from 89 programs and eligible for 3-year surveys; 600 participated (60%; RS 293, CEP 307). Aim 3: For client qualitative interviews, we approached 163 consecutive 3-year survey participants stratified by depression, race/ethnicity, gender and intervention; 104 participated (64%). For staff, we notified 289 completing 12 month surveys and used purposive follow-up stratified by community, service sector and intervention, to complete 51 interviews. Aim 4: We interviewed 49 county and community leaders planning HNI and 14 of 34 leaders attending a national briefing.

Data Sources: Self-report surveys (Aims 1 and 2) and semi-structured interviews (Aims 3 and 4).

Measures: Client outcomes are poor MHRQL ($MCS-12 \leq 40$) and depression ($PHQ-8 \geq 10$) (primary); PHRQL (12-item physical composite score (PCS-12), mental wellness, and behavioral-health hospitalization nights (community-prioritized); and use of outpatient services

(secondary). Clients and providers were asked about priorities for care and national stakeholders for responses to CPIC findings and related policy initiatives.

4-year follow-up of the 3-year sample (extension study).

The CPIC 4-year follow-up was added based on *community-stakeholder input that additional follow-up of the 3-year sample was desired to show longer-term effects on depression remission*. This follow-up built on the 3-year extension study as well as an opportunity to explore of using an existing funded cohort to recruit potential subjects into the Community and Patient Partnered Research Network (CPPRN).

Analyses plan: We will conduct 3-year end-status intent-to-treat analyses, and for 4-year follow-up of the 3-year sample, 4-year end status, with intervention status as the main independent variable, adjusted for baseline status and covariates, with response weights and multiple imputation (Aim 1); subanalyses of intervention effects within service sector at each follow-up (Aim 2); sensitivity analyses (raw data, longitudinal modeling and sector-by-intervention interactions); and thematic analyses of qualitative data (Aims 3 and 4)

7. Limitations

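### Sector is a donor stratum in the unit-level imputation only at 3 years, so the 6- and 12-month sector effects in Aim 2 can be partly attenuated and are not like for like with the 3-year ones

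*Combined protocol and SAP*

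**What the plan says.** Appendix A3 (Unit-Level Multiple Imputation) first models the probability of response at each wave. In the second step, "we stratified cases based on the quintiles of the propensity scores and used the approximate Bayesian bootstrap to select donors". The procedure runs wave by wave "with imputations stratified by two intervention arms", so every donor comes from the recipient's own arm.

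The waves differ in how sector enters:

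- **6 months.** The response model uses screener characteristics ("age, gender, ethnicity, health insurance, and type of screening program") and baseline clinical and service-use variables. No sector stratum is named for the donor step.
- **12 months.** "The 12-month models included additional variables: community, PHQ-8 assessed at screener, mental wellness, homeless status at baseline". I read this as the 6-month set plus these four. Again no sector stratum is named.
- **3 years.** Donors are drawn "with additional stratum variable sector (social-community screening sector vs healthcare Screening Sector) in Step 2".

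Section 6 (CPIC 3-Year extension) states Aim 2 as: "Compare effects of CEP and RS at 6, 12, and 36 months for CPIC participants enrolled in healthcare or community-based service sectors". Its analysis plan provides for "subanalyses of intervention effects within service sector at each follow-up (Aim 2") and for "sensitivity analyses (raw data, longitudinal modeling and sector-by-intervention interactions").

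The documents do not say which imputed data sets feed Aim 2 at 6 and 12 months, or whether those waves were imputed again once sector became a donor stratum.

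**The concern.** A quintile of response propensity groups clients who were about equally likely to respond. Within an arm that is enough, under the plan's missing-at-random assumption, for the arm's overall mean. It does not protect the mean of a subgroup inside the cell. Two clients in one quintile can belong to different sectors, and the missing one then draws from the mixed pool. Having program type in the response model separates the sectors only as far as program type predicts response.

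Aim 2 is about the subgroup. At 6 and 12 months the imputed part of each sector's effect leans toward the other sector's effect; at 3 years it does not. A sector difference that is constant over time would look smaller at the first two follow-ups, and a change of method could be read as divergence between sectors. The sector-by-intervention interaction inherits the same shrinkage if it is run on the same imputed data.

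**Working it through.** **Response figures reproduced (Section 6 and Appendix A1, A2).** 6 months: 759/1,093 = 69.4% (stated 69%). 12 months: 733/974 = 75.3% (stated 75%). 3 years: 600/1,004 = 59.8% (stated 60% in Section 6; A1 also gives 1,014 and 59%). 3-year analytic sample: 1,004 − 24 = 980, as stated.

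**Imputed share**, f = 1 − completers/analytic sample, taking all completers to lie in the analytic sample:

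- 6 months: (1,018 − 759)/1,018 = 259/1,018 = 25.4%. The arm counts in A1 sum to 380 + 359 = 739, which gives 279/1,018 = 27.4%. The other outcomes in A1 fit 759 better: 759 + 12 + 321 + 3 = 1,095 against 1,093 approached, whereas 739 gives 1,075.
- 12 months: (1,018 − 733)/1,018 = 285/1,018 = 28.0%.
- 3 years: (980 − 600)/980 = 38.8%, but with sector as a donor stratum.

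A3 does not impute for the deceased. If the 3 deaths reported at 6 months and the 5 at 12 months were all in the sample, the shares are 256/1,015 = 25.2% and 277/1,010 = 27.4%.

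**Donors that carry no sector information.** With equal response in the sectors, the estimated effect in sector s is (1 − f)·Δs + f·Δpooled. The pooled term cancels in the difference:

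estimated difference = (1 − f)(Δ1 − Δ2).

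This does not depend on the sector split. The retained fraction is 1 − 0.254 = 0.746 at 6 months and 1 − 0.280 = 0.720 at 12 months.

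Illustration with hypothetical effects of −10 and 0 points, equal sectors (pooled −5), 6 months: 0.746 × (−10) + 0.254 × (−5) = −8.7, and 0.254 × (−5) = −1.3. The difference is 7.5 points instead of 10 (before rounding, 7.46).

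**Donors that carry some sector information.** A simulation of the described hot deck assumed 1,018 clients, equal arms and sectors, effects of −15 and 0 points, 5 imputations and 400 runs. It gave these retained fractions:

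| Log-odds of response by sector | 6 months, no sector stratum | 6 months, sector stratum | 12 months, no sector stratum | 12 months, sector stratum |
|---|---|---|---|---|
| 0 | 0.780 | 1.022 | 0.667 | 0.975 |
| 0.4 | 0.756 | 0.989 | 0.722 | 1.012 |
| 0.8 | 0.865 | 1.001 | 0.837 | 1.033 |
| 1.5 | 0.922 | 1.018 | 0.934 | 0.995 |

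Standard errors are 0.018 to 0.026. The 0.667 is nearly three standard errors below 0.720, which the algebra fixes for that setting, so I treat the shortfall as simulation error. A separate simulation with 300,000 clients retained 0.73 to 0.96. I take the range from that upper figure and the algebraic lower one: 0.72 to 0.96 retained, or 4% to 28% lost. At the 3-year share, with sector as a stratum, the first simulation retained 0.946 to 0.992 (standard errors 0.025 to 0.030), consistent with no material loss.

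**Apparent growth by 3 years of a constant true difference:** 1/0.96 = 1.04 to 1/0.72 = 1.39, that is 4% to 39%.

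**Donor cells after the fix** (2 arms × 5 quintiles × 2 sectors = 20, on average): 759/20 = 38 (739/20 = 37) at 6 months and 733/20 = 37 at 12 months, against 600/20 = 30 at 3 years.

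**The case against.** Four objections deserve weight.

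- **Sector is not absent at 6 and 12 months.** Program type is in the 6-month response model and, on the natural reading, the 12-month one. This stands, and it is why the loss is partial and may be as low as 4%.
- **The plan has a check.** Raw-data analyses use no donors, so comparing them with the imputed results would expose the problem. This stands, but raw data rest on observed cases and cannot replace a sound imputation.
- **The exposure is partly unknown.** Aim 2 came with the extension, and the waves may have been imputed again. Appendix A4 describes the 12-month analysis as an unweighted repeated-measures model on available data. On the other side, A3 says that multiple-imputation inference was used throughout, A4 says that the 6-month analysis accounts for imputation, and A4 adds a weighted 12-month endpoint analysis. The point is therefore conditional on the imputed waves being used.
- **The shift is small beside the precision.** Table 4 gives a detectable difference of 9.98 to 10.92 points for the whole sample. With equal sectors, multiplying by √2 gives about 14 to 15 points within a sector, and by 2 about 20 to 22 for the interaction. A drop from 10 to 7.5 would rarely change a test result. That limits the consequence, but the bias has a known direction and the confidence intervals do not show it.

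A reader might infer that the early and 3-year sector effects cannot be compared at all, or that a sector difference at 3 years could come from imputation alone. Neither is supported. About three quarters of the 6- and 12-month records are observed, and the mechanism shrinks a true difference without creating one. If the sectors have equal effects, it introduces no bias.

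**Conclusion.** The point holds in a limited form. As written, Appendix A3 gives sector a place in the donor strata only at 3 years, while Aim 2 needs sector effects at all three follow-ups. Where the 6- and 12-month imputed waves are used, a true between-sector difference in effect is attenuated by roughly 4% to 28%, toward the pooled effect. The upper end (25.4% or 27.4% at 6 months, 28.0% at 12 months) assumes that the quintiles carry no sector information and that response is equal across sectors. The lower end assumes that program type predicts response strongly. The documents give neither that strength nor the sector split, so the direction is firmer than the size.

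The finding does not extend to the overall CEP-RS comparison: donors stay within arm at every wave, and nothing here shows bias in the pooled effect. It concerns one stated aim, labelled subanalyses, at two of its three time points.

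**What to change.** State which imputed data sets feed Aim 2 at 6 and 12 months. Unless it has already been done, repeat the unit-level imputation of both waves with sector added to the Step 2 strata, as at 3 years, and merge cells that are too thin. Use these data sets for every Aim 2 analysis that relies on imputed waves, including the sector-by-intervention interaction. Report the planned raw-data sector effects at each follow-up beside the imputed ones, so that a reader can see how far the imputation moves them.

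The cost is a rerun of a step the team has already applied, with donor cells about half as large. On average they would still be larger than those accepted at 3 years, although an uneven sector split or the low-response quintiles would make some cells thinner.
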